**• Severity /Toxicity grade**

- Severe
- Moderate
- Mild

**• Relationship**

- Definitely Related
- Probable
- Possible
- Unrelated

**• Outcome**

- Condition Deteriorated
- Still Present
- Improving
- Recovered with Sequela
- Recovered
- Other

Serious AE are defined as the following:

- Medically significant events (e.g., intensive treatment in ER or at home for allergic bronchospasm)

**ION04ED**

- life threatening
- requiring hospitalization
- resulting in death
- resulting in a disability
- resulting in a congenital abnormality

Similar tables will be presented for serious adverse events. Deaths will be reported as AE term in the CRF. Deaths and other serious adverse events will be listed.

 **Clinical laboratory tests**

The following laboratory tests will be performed at different visits as indicated in the flow chart in [section 3](#) above

- Hematology including complete blood count (CBC) with differential
- Chemistry
- Urine Analysis
- Endocrine Tests

All results corresponding to laboratory evaluations will be presented in IU units. The laboratory results will be listed by treatment cohorts, subject and visit. Abnormal results will be flagged as H or L based on values being above or below the normal range respectively. Values within the normal ranges will be flagged as N.

The frequency of number of incidences of laboratory abnormalities will be displayed by parameter and treatment cohort with respect to the classification of values based on the normal range. Descriptive statistics will be presented for laboratory results with respect to treatment cohort and visit. Further, the change from baseline at each post dose visit will be presented descriptively in accordance to the plan of data collection. Descriptive statistics for the change from baseline to the last available on treatment visit will also be presented. Shift tables will be presented for each analyte to assess the change in abnormalities over visits.

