5.2.1 Dose Limiting Toxicity

A DLT is defined as the occurrence within the first 4 weeks following a single administration of *hMaxi-K* of an unacceptable toxicity, as described below. Adverse events for cardiovascular, blood chemistry, complete blood count, or urine categories of adverse events will be graded according to the criteria provided in [Appendix A](#).

No acute toxicity was seen in the preclinical studies with administered doses up to 1000 μg (approximately 1500 $\mu\text{g}/\text{kg}$) or in men and women given doses up to 16000 μg . Potential toxicities would be those that could occur due to enhanced efflux of K^+ with resultant decreased intracellular Ca^{++} concentration thus altering smooth muscle function in diverse organ systems.

The following criteria will be used to define:

DLT:

- 1) Any adverse events of Grade 2 or higher in the cardiovascular category of adverse event criteria listed in [Appendix A](#);
- 2) Any adverse events of Grade 2 or higher in the blood chemistry, complete blood count, or urine categories of adverse event criteria listed in [Appendix A](#).

- 3) Penile pain and/or erection that persists for more than four hours after gene transfer;
- 4) Change in random hormone levels greater than 2 times the upper or lower limits of normal at any time post dosing..

Stopping Rule

If within 4 weeks following the single administration of *h*Maxi-K, if any participant experiences a grade 3 or higher dose limiting toxicity, no additional participants will be accrued and no further doses of *h*Maxi-K (or placebo) will be administered. Clinical data regarding the event will be collected, reviewed, and discussed with the Ethics Committee (EC) and Kuwait Ministry of Health (MOH). After review of these data with EC and MOH the clinical study may resume only with concurrence of EC and MOH.

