9.0 Adverse Events Definitions and Monitoring

9.1 Adverse Event

An adverse event is any unfavorable and unintended diagnosis, symptom, sign (including an abnormal laboratory finding), syndrome or disease which either occurs during the study, having been absent at baseline, or, if present at baseline, appears to worsen.

A treatment emergent adverse event (TEAE) will be considered an event that is temporally associated with the use of the study drug, whether or not considered related to the study drug.

Examples of AEs are as follows:

- Changes in the general condition of the participant
- Subjective symptoms offered by or elicited from the participant
- Objective signs observed by the Investigator or other study personnel
- All concurrent diseases that occur after the start of the study, including any change in severity or frequency of preexisting disease
- All clinically relevant abnormalities in laboratory values or clinically relevant physical findings that occur during the study.

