 **Adverse Events**

All the adverse events will be coded using the MedDRA Version 19.1. All the information collected in the AE form in the CRF and the preferred term, and system organ class corresponding to each reported term will be presented as a listing. In addition to this SAEs will be presented as a separate listing.

An overall summary table for the adverse events will be presented. All TEAEs recorded during the study will be further summarized in detail. The incidence of adverse events will be summarized by system organ class and preferred term within system organ class overall and by severity, relationship, outcome, action taken separately and DLT.

Summary tables corresponding to the AEs will contain the incidence of events and the number and percentage of subjects experiencing an adverse event. The percentages will be calculated with respect to the total number of subjects in the safety population. While counting the number of subjects, a subject with more than one adverse event with the same preferred term will be counted only once using the incidence with highest severity (severity, action taken and DLT tables), or strongest relationship to study treatment and most severe outcome for the respective tables. The descending order of the above characteristics will be considered as below

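### SAP 9.4 derives no Appendix A grade or DLT flag from the laboratory values, so in the visible text laboratory DLTs are counted only from adverse event records

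*SAP*

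**What the plan says.** **Protocol.** Section 5.2.1 lists four DLT criteria, and two rest on laboratory data. Criterion 2, which points to Appendix A, reads "Any adverse events of Grade 2 or higher in the blood chemistry, complete blood count, or urine categories of adverse event criteria". Criterion 4 concerns hormone levels beyond twice a limit of normal. The stopping rule in the same section acts on a DLT of Grade 3 or higher within 4 weeks of dosing. Section 9.1 counts an abnormal laboratory finding as an AE, and its list of examples includes "All clinically relevant abnormalities in laboratory values or clinically relevant physical findings that occur during the study". Sections 9.4 and 9.5 require events in the toxicity table to be graded, all observed AEs to be recorded, and events meeting the four criteria to reach the sponsor within 24 hours.

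**SAP 9.4, Clinical laboratory tests.** "Abnormal results will be flagged as H or L based on values being above or below the normal range respectively". In-range results get the flag N. Abnormalities are then tabulated by parameter and cohort "with respect to the classification of values based on the normal range". The section adds listings, descriptive statistics by visit and change from baseline. On shifts it says: "Shift tables will be presented for each analyte to assess the change in abnormalities over visits". On units it says: "All results corresponding to laboratory evaluations will be presented in IU units". Appendix A is not mentioned.

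**SAP 9.4, Adverse Events.** The AE outputs come from the CRF's AE form. Incidence is summarised "overall and by severity, relationship, outcome, action taken separately and DLT". This is the only place in the visible SAP analysis text where DLTs are counted.

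**The concern.** A laboratory DLT is defined by a numerical threshold, and the trial collects the numbers. Chemistry, blood count and urinalysis are measured at Weeks 1 and 4 (protocol 6.6), within the 4-week DLT period. Yet the SAP never applies the thresholds to those results in its laboratory section. The count depends on each qualifying value having first been entered as an AE.

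The example in protocol 9.1 leaves room for judgement at that step. If a Grade 2 value is judged not clinically relevant and is not entered, it is missing from both the AE and DLT tables. In the laboratory tables it looks the same as a trivial excursion. Safety is the protocol's primary objective (section 2.0), so the DLT count by dose should be reproducible from the data.

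**Working it through.** The plan states no figure to reproduce here. The check sets the definitions side by side and applies Appendix A to example values.

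**1. Can the flag separate grades?** Appendix A grades ALT as above ULN to 2.5 x ULN (Grade 1), above 2.5 to 5 (Grade 2), above 5 to 20 (Grade 3) and above 20 (Grade 4). The SAP flag is H for anything above normal.

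| ALT (x ULN) | SAP flag | Appendix A grade | Reaches DLT grade (2+) | Reaches stopping-rule grade (3+) |
|---|---|---|---|---|
| 1.2 | H | 1 | no | no |
| 3 | H | 2 | yes | no |
| 6 | H | 3 | yes | yes |
| 21 | H | 4 | yes | yes |

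All four values share one flag.

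**2. Do the shift tables show worsening?** Exclusion criterion (n) allows hepatic markers above twice ULN at screening with the sponsor's written consent. Such a man is H at baseline. If his ALT rises to 6 x ULN he reaches Grade 3, but a shift table built on these flags records H to H, which is no change.

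**3. Can a DLT-grade value be flagged normal?** Appendix A grades haemoglobin by absolute level or by fall: at least 3.5 g/dL is Grade 2 and at least 4.5 g/dL is Grade 3. The documents give no normal range, so the lower limit is varied as an assumption.

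| Haemoglobin (g/dL) | Fall | Grade | Flag if lower limit is 12.5 | 13.0 | 13.5 | 14.0 |
|---|---|---|---|---|---|---|
| 17.0 to 13.5 | 17.0 − 13.5 = 3.5 | 2 | N | N | N | L |
| 17.5 to 13.0 | 17.5 − 13.0 = 4.5 | 3 | N | N | L | L |

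Under several plausible limits, a Grade 2 or Grade 3 fall is shown as normal.

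**4. Hormone criterion 4.** This criterion is not worded as an AE and has no Appendix A row, so Appendix A grading alone would miss it. SAP 9.4 treats endocrine results like the other laboratory tests and derives no flag for the criterion. The time window is also inconsistent within section 5.2.1: the general DLT definition covers the first 4 weeks, while criterion 4 covers any time after dosing. This matters because post-dose hormones are measured only at Visit 3 (Week 1) and Visit 7 (Week 24). The Week 24 values count under one reading and not under the other.

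**5. Does the AE route keep the grade?** Only in part. The SAP's severity order has three levels (severe, moderate, mild), while Appendix A has a fourth, potentially life-threatening.

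**6. Units.** Ten Appendix A rows are multiples of ULN (PT, PTT, LDH, bilirubin, CPK, creatinine, AST, ALT, GGT, alkaline phosphatase), so units do not affect them. Rows such as haemoglobin (g/dL), sodium and potassium (mEq/L) and BUN (mg/dL) need a conversion rule if results are held in the unit system that the SAP names.

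**7. Effect of one uncounted man.** In an 11-man dose arm, 1/11 = 0.091, or 9.1 percentage points. In the 13-man placebo arm, 1/13 = 0.077, or 7.7 percentage points.

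**The case against.** The strongest defence is that the SAP follows the protocol's own definition. Criterion 2 is worded as an adverse event, so counting laboratory DLTs through AE records is consistent with it. Recording, grading and 24-hour reporting are all required. The clinically relevant wording in section 9.1 sits in a list of examples, and examples need not narrow the definition above them. This stands. A derived count is a cross-check on the protocol's definition and does not replace a wrong analysis.

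Three stronger readings are tempting, and the documents do not support them.

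- A reader might infer that investigators are free to decide whether a laboratory DLT is entered. They are not: the duties in 9.1, 9.4 and 9.5 are mandatory. The discretion is limited to what the clinical relevance example leaves open.
- A reader might infer that laboratory values are graded nowhere in the planned outputs. That cannot be established, because the table list in SAP section 10 is not visible and the output shells are separate documents.
- A reader might want to state the share of laboratory DLTs that would be missed. Any such figure is one minus an assumed reporting share, and the documents give no reporting share.

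It is also fair to say that listings, descriptive statistics and change from baseline will show the raw results, and in a 35-man trial a Grade 3 value can be found by reading the listing. The stopping rule acts on single events as they are reported and does not wait for a SAP table. No decision threshold on the DLT rate is specified. These points limit the consequence, but none of them yields a DLT count derived from the laboratory data.

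**Conclusion.** The concern holds in a limited form. The text of SAP 9.4 classifies laboratory values only against the normal range and derives neither an Appendix A grade nor a DLT flag. In the visible SAP, DLTs are summarised only from AE-form records. A Grade 2 or higher value judged not clinically relevant could therefore go uncounted. The high/low/normal tables could not expose it, since they neither separate Grade 1 from Grade 3 nor show worsening from an abnormal baseline.

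The only firm size is 9.1 percentage points per uncounted man in an 11-man arm; the number of such men is unknown. The ALT result follows directly from Appendix A. The haemoglobin result depends on the assumed lower limit of normal. The conclusion also assumes that the unseen tables and shells contain no graded laboratory output. This is a cheap improvement to the safety analysis, and it does not show that the planned AE-based count is invalid.

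**What to change.** Amend SAP 9.4 as follows:

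- Derive the Appendix A grade for each collected analyte with an applicable row. CPK and phosphate have rows but are not in the protocol 6.6 panel, so they drop out. Convert to Appendix A units where the row is not a multiple of ULN.
- State how glucose is handled. The hyperglycaemia row is limited to non-fasting samples from men without diabetes, while diabetic men are eligible and fasting is specified only at screening.
- Derive a separate flag for hormone criterion 4. The two time windows in protocol 5.2.1 must be reconciled first.
- Present baseline-to-worst-grade shift tables by dose group.
- Before unblinding, reconcile laboratory-derived Grade 2 or higher values and hormone flags with the DLTs on the AE form, and document each discrepancy.

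The cost is SAP wording, programming and reconciliation work. The grading uses results already collected. If fasting status was not recorded after screening, glucose may have to be left ungraded or graded under a stated assumption.

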 **Electrocardiogram**

As part of the analysis for this safety endpoint, in addition to the analysis suggested in [section 9.2](#) above, changes from baseline at each post dose visit will be presented. Number and percentage of subjects reporting abnormalities will further be tabulated with respect to treatment cohort and visits for both the over reader and site evaluations. Shift tables will also be presented to study the change in abnormalities over the visits.

 **Physical examinations and vital signs**

In addition to the analysis mentioned in section 9.2, the descriptive statistics for change from baseline at post dose visits will be presented for the below parameters

- Heart rate
- Blood pressure
- Weight
- Oral Temperature

Further, the number and percentage of subjects reporting abnormalities for above parameters and during physical examination of the penis will be tabulated with respect to treatment cohort and visits.

 **Pharmacokinetics Evaluations**

[figure not shown]

## STATISTICAL ANALYSIS PLAN

### ION04ED

At V2 –V7, plasma specimens will be collected to assay for the presence of hSlo DNA by PCR. This data will be listed and presented descriptively. No PK analysis will be performed.

[figure not shown]
#### 10. Listings, Tables and Figures

## STATISTICAL ANALYSIS PLAN

ION04ED

[figure not shown]

## STATISTICAL ANALYSIS PLAN

---

ION04ED

[figure not shown]

[figure not shown]
COG NUB

ION04ED

## STATISTICAL ANALYSIS PLAN

---

## 11. Software

SAS® Version 9.2 or higher will be used for all data analysis

